3.4 Outcomes and variables

Because this is an exploratory study, no distinction is be made between primary and secondary outcomes.

Name	Method and metric	Time points of data collection		
Blistering Time	 Visual inspection Duration from start of suction pressure to appearance of first vesicles in minutes Duration from start of suction pressure to development of full blister in minutes (Appendix 4) 	Visit 3, Visit 5		
Skin surface Temperature	- Measurement with Skin- Thermometer ST 500 (Courage+Khazaka electronic GmbH) - Means of duplicate measurements per skin area in °C per skin area	Visit 3, Visit 5		
Stratum corneum hydratation (SCH)	- Corneometer CM 825 (Courage + Khazaka, Cologne, Germany) (Appendix 5) - Means of duplicate measurements per skin area in arbitrary units	Visit 1, Visit 2, Visit 3, Visit 4, Visit 5, Visit 6		
Epidermal and dermal hydratation	- Measurement with MoistureMeterEpiD (Delfin Technologies) (Appendix 6) - Percentage of tissue water (0- 100%) (0,5mm measurement depth)	Visit 1, Visit 2, Visit 3, Visit 4, Visit 5, Visit 6		
Epidermal thickness	- OCT (Thorlabs, Lübeck, Germany), measurements according to Trojahn et al. 2015 µm) (Appendix 8)	Visit 1, Visit 3, Visit 5, Visit 6		

Name	Method and metric	Time points of data collection
Age	Checking by looking at the ID card (metric)	Screening
Body temperature	Clinical thermometer in °C	Screening
Heart rate	Beats per minute (bpm)	Screening
Blood pressure	Millimeters of mercury (mmHg)	Screening
BMI (body height and weight)	kg/m ²	Screening
Phototype	Categories I, II, III	Screening

Both arms will be subdivided in two investigational areas, called "Area A" (upper part of the middle of the right volar forearm) respectively "Area C" (upper part of the middle of the left volar forearm) and "Area B" (lower part of the middle of the right volar forearm) respectively "Area D" (lower part of the middle of the left volar forearm) (Figure 1).

After 4 weeks (Visit 3) 2 suction blisters (Appendix 4) will be raised at the investigational Areas A or B at the right volar forearm (Figure 2). Another 2 suction blisters will be raised at the left volar forearm at the investigational Areas C or D (Figure 2). The allocation of the respective area for suction blister induction is decided via a randomization list.

After 4 additional weeks (Visit 5), 2 more suction blisters will be raised in each of the remaining so far non-blistered investigational Areas.

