After the blister has been raised, the blister fluid will be punctured and a dressing applied to allow the wound to heal. The skin areas where suction blisters have been raised after 4 weeks will not be treated during the following 8 weeks.

Before any measurements or induction of the suction blisters, the study volunteers will be requested to acclimatize for 30 minutes at 40 to 60 % relative humidity and a temperature of 20 to 22 °C with having both forearms uncovered.

Sequence of measurements (Visit 1, 2, 3, 4, 5 and 6)

- (1) Skin surface temperature
- (2) Stratum corneum hydration (SCH)
- (3) Epidermal and dermal hydration
- (4) Skin thickness

Measurements will be performed two times per measurement area. Every value will be recorded separately.

Figure 1. Localization of investigational skin areas

[figure not shown]
[figure not shown]

Figure 2. Localization of suction blisters

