3.7 Recruitment

Subjects will recruited via advertisements and/or contacted directly.

4 Methods: Assignment of interventions

There will be a concealed random allocation of the treatment arm (left vs. right) and area of suction blister induction ("Area A"/ "Area C" vs. "Area B"/ "Area D").

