4.1 Allocation Sequence Generation

Two independent simple randomization lists (left vs. right arm and "Area A"/ "Area C" vs. "Area B"/ "Area D") will be created by the data manager not involved in the study. The data manager will also prepare sequentially numbered opaque sealed envelopes containing the allocation.

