5.1 Data collection methods

All data collectors will be trained in obtaining accurately the variables of interest. Paper source data (SD) will be used to document all study variables of interest (data collection forms see appendix 3).

Medical examination

The medical examination performed before inclusion will include a subject's interview on her medical history and a clinical examination, to make sure of the subject's eligibility.

Suction blister creation

The Suction blister model is an artificial and controlled technique for dermal-epidermal separation. Over the course of this study a total of 8 suction blisters with 8 mm in diameter are produced at the middle of the volar forearms of one volunteer. The comparisons of the blistering times (in minutes) will be used as outcome to detect possible treatment effects. Two suction blisters will be induced on each investigational area for two independent measurements of the blistering time. The technical procedure of suction blister wound creation is presented in the SOP Appendix 4.

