5.3 Statistical methods

Demographic and other characteristics will be described using mean and spread parameters or proportions. The skin measurement results including the time(s) to blistering will be described using medians and interquartile ranges per skin area and time and displayed in grouped bar graphs. No statistical tests will be applied.

6 Methods: Monitoring

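### Section 5.3 summarises results by anatomical skin area, but petrolatum is randomised by forearm, so the only planned analysis does not specify a petrolatum-versus-control summary

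*Combined protocol and SAP*

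**What the plan says.** Section 5.3 gives the grouping rule for all skin outcomes: "The skin measurement results including the time(s) to blistering will be described using medians and interquartile ranges per skin area and time". It adds grouped bar graphs and rules out statistical tests. Treatment, control, arm and petrolatum are not mentioned.

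Section 3.4 defines the areas: "Both arms will be subdivided in two investigational areas", with A and B on the right volar forearm and C and D on the left. The outcome table uses skin area for these sites, for example for stratum corneum hydration: "Means of duplicate measurements per skin area in arbitrary units".

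Section 3.3 assigns petrolatum to one randomly selected forearm and leaves the other untreated. Section 4 describes a "concealed random allocation of the treatment arm (left vs. right) and area of suction blister induction", and section 4.1 says these come from "Two independent simple randomization lists".

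Section 3.4 also takes part of the treated forearm off petrolatum after Visit 3: "The skin areas where suction blisters have been raised after 4 weeks will not be treated during the following 8 weeks". At Visit 5, blisters are raised only in the areas not blistered before.

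The purpose is clear from section 5.1: "The comparisons of the blistering times (in minutes) will be used as outcome to detect possible treatment effects".

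**The concern.** The grouping factor in the analysis section is not the factor that was randomised. Side is randomised separately for each subject, so Area A is petrolatum skin in some women and control skin in others, and the same holds for B, C and D. A median for Area A at Visit 3 therefore estimates neither condition. With no tests, model or primary outcome, these medians are the entire analysis, and as worded they do not address the aim in section 2.2.

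Most analysts would regroup by arm. That leaves a second choice open. From Visit 3 on, one of the two sites on the treated forearm is no longer treated and is healing. Whether that site enters the Visit 4-5 hydration summaries, and the Visit 5 thickness and skin temperature summaries, changes what those summaries estimate. Assessors are unblinded (section 4.3), so the choice is better made before the data are seen.

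**Working it through.** **Inputs.** 12 subjects (3.6); two areas per forearm (3.4); side and first-blistered area from two independent simple lists (4.1), taken here as 1:1; two blisters per area and 8 in total (5.1); visit windows from Table 1 (3.5).

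**Structure check.** 4 areas × 2 blisters = 8, which matches the total in section 5.1. The investigational areas are therefore the four sites A-D. The sample size of 12 has no formula behind it to reproduce.

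**Grouping by area, hydration at Visits 2-3 and thickness at Visit 3.** Each label has 12 readings. The number treated is Binomial(12, 1/2): mean 6, and 3 to 9 with probability 0.96.

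**Grouping by area, blistering time.** At a given visit a label is blistered in Binomial(12, 1/2) subjects, mean 6. The number both blistered and treated is Binomial(12, 1/4), mean 3, so on average 3 are treated and 3 control.
- Probability that a given cell contains both conditions: Σ P(K = k)(1 − 2 × 0.5^k) over k = 2 to 12, with K ~ Binomial(12, 1/2), = 0.94.
- Probability that a given label has no treated blistering time: 0.75^12 = 0.032.
- Probability that at least one of the four has none: 4(0.75^12) − 6(0.5^12) + 4(0.25^12) = 0.125.

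**Grouping by arm.** There are 12 treated and 12 control forearms per visit, paired within subject. In a simulation with an assumed effect of 1.0, between-subject SD 1 and within-arm SD 0.5, the median within-subject difference in Visit 3 blistering time averages 1.00 (SD 0.24).

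**Visits 4-5, if blistered sites are still measured.** Each treated forearm has one site on petrolatum and one off it, so 12 of 24 treated-forearm sites are off treatment.
- Time off at Visit 4: days 40-44 minus days 26-30 = 10 to 18 days.
- Time off at Visit 5: days 54-58 minus days 26-30 = 24 to 32 days.
- Let r be the share of the effect that persists off treatment. The documents give no value, so 0 to 1 is assumed. Pooling both sites shows (1 + r)/2 of the effect: 50% at r = 0, 75% at r = 0.5, 100% at r = 1. This assumes roughly symmetric values and no effect of healing on the treatment difference. With skewed (exponential, independent) values the figure at r = 0 is 62%.

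**Precision cost of using only the unblistered site.** Simulation of 40,000 trials of 12, normal values with unit SD, r = 0; entries are the SD of the treated-minus-control summary.

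| Assumed within-subject correlation | Arm medians, both sites pooled | Arm medians, unblistered site | Median paired difference, unblistered site |
|---|---|---|---|
| 0.3 | 0.32 | 0.43 | 0.41 |
| 0.5 | 0.29 | 0.38 | 0.34 |
| 0.8 | 0.22 | 0.28 | 0.22 |

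Comparing the two arm-median columns, the increase is 0.43/0.32 = 1.34, 0.38/0.29 = 1.31 and 0.28/0.22 = 1.27. The unblistered-site estimate averages 1.00 of the effect for every r tried.

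**The case against.** The strongest reply is that the intent is plain. The aim, the untreated control arm, the randomised side and section 5.1 all point to a treatment comparison, and an analyst who ignored allocation in a split-body trial would be making an unlikely mistake. The formally defined term is also investigational area, so skin area in 5.3 might loosely mean treated or untreated skin. The intent is conceded. The looser reading is possible, but no visible text gives it, and section 3.4 uses skin area for the anatomical sites.

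A reader might infer that the plan would lose the treatment effect altogether, because a right-minus-left contrast (A against C) averages zero under 1:1 randomisation of side. The documents do not support that as an expected loss: 5.3 names no such contrast, and side and area are known for each subject, so nothing is irrecoverable.

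A reader might also infer that the Visit 4-5 effects will be diluted. That does not follow either. Dilution needs an analyst who pools the two sites, which 5.3 does not direct; section 3.3 already distinguishes 4 from 8 weeks of application, and summarising by treatment, area and visit would avoid it. It also needs blistered sites to be measured again. Section 3.4 lists measurements at Visit 6, when every site has been blistered, which suggests that they are; Table 1 omits these Visit 6 measurements, and the figures and data collection forms are not available. The range for r includes no loss at all.

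Finally, this is a 12-subject exploratory study without tests. That limits the severity, but it also makes the descriptive grouping the whole analysis.

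**Conclusion.** The point holds as a gap in the specified analysis. Followed as written, 5.3 produces cells that are on average half treated and half control and gives no petrolatum-versus-control summary, although one is clearly intended. This rests on reading skin area as the sites A-D and on 1:1 randomisation of side.

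The Visit 4-5 part is conditional. If previously blistered sites are still measured and both sites of an arm are pooled, the summary shows 50% to 100% of the effect, for an assumed persistence of 0 to 1 and roughly symmetric values. Blistering time is outside this second part, because Visit 5 blisters are raised only at sites not blistered before. The plan should be corrected, but the data already collected under it would allow the right analysis.

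**What to change.** Change the wording of 5.3 as follows.

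1. Summarise every skin measurement, blistering time included, by treated versus control arm and visit.
2. Report the median and interquartile range of the within-subject treated-minus-control difference.
3. If areas blistered at Visit 3 are measured afterwards, base the Visit 4-5 hydration comparisons and the Visit 5 thickness and skin temperature comparisons on the area not blistered at Visit 3. This gives one treated-control pair per subject, n = 12.
4. Report previously blistered areas separately, labelled as off treatment and healing. This covers all areas at Visit 6, if measured.

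No change in conduct is needed. Arm and first-blistered area are known for each subject, and section 3.4 says "Every value will be recorded separately".

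The cost is one area per arm instead of two at Visits 4-5. The spread of the arm difference in medians rises by about one third under the assumed correlations, and the paired difference recovers part of this. Blistering time loses nothing.

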2.2 Objectives

The main aim of this study is to investigate in a suction blister model, whether the use of a basic skin care formulation increases the mechanical integrity/adhesion of the dermo-epidermal junction.

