2.3 Trial design

Exploratory randomized controlled study with a split body design on two investigational areas of the anterior side of both forearms.

3 Methods: Participants, interventions, and outcomes

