3.6 Sample size

Due to the explorative character of this study, a formal sample size estimation is not performed. It is planned to include 12 healthy female subjects.

Subject replacement

In this study, a subject withdrawn from the study for any reason will be replaced.

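### Section 5.3 plans neither an estimate of the within-woman petrolatum effect on blistering time nor any measure of its uncertainty, although 2.2 asks whether adhesion increases

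*Combined protocol and SAP*

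**What the plan says.** The main aim in 2.2 is to find out "whether the use of a basic skin care formulation increases the mechanical integrity/adhesion of the dermo-epidermal junction". Section 2.3 describes the trial as: "Exploratory randomized controlled study with a split body design on two investigational areas of the anterior side of both forearms". Under 3.3 one forearm receives petrolatum and the other is left untreated, so every woman supplies her own control. Section 5.1 gives blistering time its purpose: "The comparisons of the blistering times (in minutes) will be used as outcome to detect possible treatment effects".

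Section 5.3 states the whole analysis. The skin measurements, blistering times included, "will be described using medians and interquartile ranges per skin area and time and displayed in grouped bar graphs". It then closes: "No statistical tests will be applied". No paired difference, confidence interval or rule for reading the results appears elsewhere in the document.

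On size, 3.6 says "It is planned to include 12 healthy female subjects" and that "a formal sample size estimation is not performed". Section 3.4 declines to name a primary outcome and gives two blistering-time definitions, first vesicles and full blister, both measured at Visits 3 and 5.

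**The concern.** The question is about an effect, and the design is built to estimate that effect within each woman. The planned summary stops short of it. An IQR for one skin area describes how blistering times differ between women, plus replicate variation if the two blisters are not averaged first. It does not shrink as women are added, and it is the same whether the two forearms of a woman agree closely or not at all. It therefore cannot show how precisely the petrolatum effect has been estimated.

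A reader is left to compare medians by eye. A gap between medians that arose by chance and one that reflects a consistent shift within women can look alike. Section 7.8 commits the results to a trial register and a journal, so readers will draw conclusions from this display.

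**Working it through.** **Plan's own figure.** There is none to reproduce: the document gives no effect size, SD, alpha or power, and 12 is stated without a calculation.

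**Inputs.** n = 12 pairs (3.6, 2.3, 3.3); two blisters per area (5.1); two blistering-time definitions and two blistering visits (3.4). The correlation r between a woman's two forearms is not given, so it is an assumption, run from 0 to 0.9. Data are taken as normal with equal SD in both arms, and results are in units of the between-woman SD. The calculation also takes the reading more favourable to the plan, that areas are regrouped as treated and untreated. Section 5.3 says only per skin area, and areas A to D in 3.4 are right and left positions, while the treated side is randomised.

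**Step 1: what medians do under no effect.** 200,000 simulated trials of 12 pairs for each r. The treated median is the larger in 50% of trials at every r.

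**Step 2: precision of the paired contrast.** The SD of the differences is √(2(1−r)). The 95% half-width for the mean difference is t(0.975, 11 df)/√12 × √(2(1−r)) = 2.201/3.464 × √(2(1−r)) = 0.635 × √(2(1−r)).

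| r | Medians differ by > 0.25 SD in favour of petrolatum, no effect | By > 0.5 SD | 95% half-width, mean paired difference | Average IQR in one arm |
|---|---|---|---|---|
| 0 | 30% | 15% | 0.90 SD | 1.2 SD |
| 0.3 | 28% | 12% | 0.75 SD | 1.2 SD |
| 0.5 | 26% | 10% | 0.64 SD | 1.2 SD |
| 0.7 | 22% | 6% | 0.49 SD | 1.2 SD |
| 0.9 | 13% | 1% | 0.28 SD | 1.2 SD |

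The half-width changes about threefold down the table (0.90/0.28 = 3.2) and the IQR does not move. The planned display looks the same whether the comparison is precise or imprecise.

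**Step 3: can 12 women support an interval?** For the median of 12 differences, the interval from the 3rd to the 10th ordered value has coverage 1 − 2·P(X ≤ 2), with X ~ Binomial(12, 0.5). This is 1 − 2(1 + 12 + 66)/4096 = 1 − 158/4096 = 96.1%. It needs neither normality nor symmetry.

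**Step 4: price of several intervals.** Two definitions × two visits = 4 intervals. If they were independent and there were no effect, at least one would exclude zero with probability 1 − 0.961⁴ ≈ 15%.

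**The case against.** The strongest reply is that the choice is deliberate and disclosed. The title, 2.3, 3.4 and 3.6 all call the study exploratory, there is no primary outcome, 5.1 speaks only of possible effects, and no efficacy claim or decision rule is planned. Descriptive reporting fits that status. This stands as a defence of having no test and no sample size calculation. It does not explain leaving out the size of the effect and its precision, which an exploratory study needs in order to show how much was learned.

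A reader might infer that 5.3 forbids any inference. It does not: it excludes tests and is silent on intervals.

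A reader might also illustrate the risk by how often most of the 12 women would favour petrolatum by chance (at least 8 of 12: 19.4%). The plan reports no such count, so the figure does not describe what readers will see.

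Finally, a reader might infer that an interval would reveal a shift of, say, 0.7 SD that overlapping IQRs conceal. That follows only for an observed shift of 0.7 SD and a high correlation; at r = 0.3 or 0 the half-widths of 0.75 and 0.90 SD exceed it. For a true shift of 0.7 SD, simulation puts the t interval above zero in 60%, 81% and 94% of trials at r = 0.5, 0.7 and 0.8, and the 3rd-to-10th interval in 42%, 62% and 79%. An interval reports precision; it does not guarantee detection.

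**Conclusion.** The point holds as a gap in reporting. The plan asks about an effect, uses a paired design to measure it, and specifies neither the paired estimate nor its uncertainty. Medians that differ by more than 0.25 SD in favour of petrolatum would arise in roughly one null trial in three to one in eight, depending on r, and the planned display gives no means of judging such a gap. These figures rest on normal data, equal SDs, 12 complete pairs and assumed correlations; the 96.1% coverage needs only independent women and continuous differences.

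A reader might go further and conclude that the study is invalid or needs a significance test. The documents do not support that: the study is openly exploratory, it can run as designed, and the data it already collects are enough to close the gap. The change is worth making before analysis.

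**What to change.** Add to 5.3:

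> For each blistering-time definition in 3.4 and each blistering visit, the two blisters per area are averaged, the within-woman difference (petrolatum minus untreated forearm) is computed, and the median difference is reported with the distribution-free interval from the 3rd to the 10th ordered difference (96.1% coverage at n = 12). All four intervals are reported, are exploratory and unadjusted for multiplicity, and no hypothesis test is performed.

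This names one interval method, so none is chosen after the data are seen, and it fixes how the two blisters are combined. It is compatible with the existing sentence on tests. The ranks 3 and 10 belong to 12 complete pairs; with another number, the ranks and coverage must be restated.

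The cost is a few lines of text, with no new data, visits or subjects. The downside is that the intervals will be wide at n = 12, and with four of them one may exclude zero by chance (about 15% if independent), so a single such interval must not be read as a finding.

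The alternative is to reword 2.2 and 5.1 as purely descriptive. That also removes the mismatch, but gives up the stated aim.

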6.1 Data monitoring

Data monitoring is not planned.

6.2 Harms

Within this trial, the following definitions of adverse events will be used:

Adverse Event (AE)

Adverse events are defined in this study as any untoward medical occurrence, unintended disease or injury, or untoward clinical signs in patients, related to the intervention. Adverse events reported to the investigator must be recorded on the adverse event page of the data collection form and should be described.

Serious Adverse Event (SAE)

Adverse Event that:

- i. leads to death;
- ii. leads to a serious deterioration in the health of the subject, that either resulted in;
- a life-threatening illness or injury, or
- a permanent impairment of a body structure or a body function; or

prolonged hospitalization; or,

medical or surgical intervention to prevent life-threatening illness or injury or permanent impairment to a body structure or a body function; or

iii. led to foetal distress, foetal death or a congenital abnormality or birth defect.

Note: Planned hospitalization for a pre-existing condition, without serious deterioration in health, is not considered a serious adverse event.

7 Ethics and dissemination

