3.3.1 Concomitant Treatments

Prohibited concomitant treatments

- Any topical drug (hyaluronan, anti-inflammatory drugs, corticoids, retinoids, vitamin C, corticoids, etc.) on investigational areas until the last assessment
- Any systemic treatment which may interfere with either investigational products or study conduct (anti-inflammatory drugs, corticoids, retinoids, vitamin C, corticoids, etc.) for more than 5 consecutive days until the last assessment
- Any treatment which may affect the blood coagulation and hemostasis (anticoagulant medications, NSAID, etc.)

Allowed concomitant treatments

The associated treatments which are considered necessary and not interfering with either investigational products or study conduct can be used on decision of the Investigator. The drug names (INN), their indication, dose and duration will be recorded in the CRF in concomitant treatments section.

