3.5 Participant timeline

Table 1. Participant timeline

	Visit 0 Screening	Visit 1 Inclusion	Visit 2	Visit 3	Visit 4	Visit 5	Visit 6
	D ₋₁₄ to D ₀	D_0	D _{14±1}	D _{28±2}	D _{42±2}	D _{56±2}	D _{66±3}
Informed consent	X						
Demography	X						
Medical history	X						
Vital signs	X						
Physical examination	X						
In-/exclusion criteria	X	X					
BMI	X						
Randomization of arms		Х					
Instruction how to treat the treatment arm		Х	Х	X	X		
Handout of products		Х		Х			
Treatment		4					
Record concomitant medication, therapies, procedures	X	Х	Х	X	Х	Х	Х
Investigational sites identification		Х					
Blister Induction*				Х		X	
Check for blister healing					Х		Х
Stratum corneum hydratation		X	Х	Х	Х	X	
Epidermal and dermal hydratation		Х	Х	Х	Х	X	
Epidermal thickness		Х		Х		X	
Record AEs		Х	Х	Х	Х	Х	Х
Return investigational products						X	

^{*}Randomization

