4.3 Blinding

Due to the nature of the intervention, neither the investigators nor the participants will be blinded.

5 Methods: Data collection, management, analysis

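### Section 6.2 defines adverse events as related to the intervention, so events judged unrelated, including deaths, need not be recorded as AEs or SAEs

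*Combined protocol and SAP*

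**What the plan says.** Section 6.2 (Harms) sets the definitions for the trial. An AE is "any untoward medical occurrence, unintended disease or injury, or untoward clinical signs in patients, related to the intervention"; the word for relatedness is underlined in the source. The recording duty follows: "Adverse events reported to the investigator must be recorded on the adverse event page of the data collection form". The SAE definition opens with "Adverse Event that" and then lists the seriousness criteria, the first of which is death.

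Other sections bear on what would be captured:

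- Table 1 in section 3.5 schedules AE recording at Visits 1 to 6, with no other definition. It also has a row, "Record concomitant medication, therapies, procedures", marked at Visits 0 to 6, and a check of blister healing at Visits 4 and 6.
- Section 3.3.1 says of allowed concomitant treatments: "The drug names (INN), their indication, dose and duration will be recorded in the CRF in concomitant treatments section".
- Section 4.3 says that "neither the investigators nor the participants will be blinded", and section 6.1 that "Data monitoring is not planned".
- Section 5.3 describes demographic data and skin measurements and mentions no AE or SAE summary.

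**The concern.** Relatedness is normally something recorded about an event. Here it decides whether an event counts at all. Someone has to judge causality before section 6.2 obliges anyone to write the event down, and the protocol does not say who judges, by what criteria or when. The investigators know which arm is treated, and no data monitoring is planned, so the visible text provides no later check on that judgement.

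At stake is whether the harms record can be reviewed. Followed as written, it holds only events already judged related. A wrong judgement of unrelatedness could be re-examined only indirectly, from a treatment entry, and not at all if no treatment was given. The subjects are women aged 65 to 85, and stable chronic conditions are allowed (section 3.2), so intercurrent events are plausible.

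The reference point for relatedness is also unclear. Section 3.3 describes the intervention as petrolatum application, while suction blistering is described under outcomes (3.4) and data collection (5.1). Read narrowly, a complication of the blister procedure might not count as related to the intervention.

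**Working it through.** The plan states no figure to reproduce on this point, and the check is one of logic and cross-reading.

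**Step 1: the definitions in section 6.2.**

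- AE = untoward event AND related to the intervention.
- Duty to record = AEs, so defined, that are reported to the investigator.
- SAE = AE AND at least one seriousness criterion.
- Hence SAE = untoward AND related AND serious. A death judged unrelated fails the second condition, so it is neither an AE nor an SAE under section 6.2.

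**Step 2: does another section widen this?**

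| Place | What it adds | Does it cure the gap? |
|---|---|---|
| 3.5, Table 1, AE row | Timing: Visits 1 to 6 | No; it relies on the definition in 6.2 |
| 3.3.1 | Four items per allowed drug: name, indication, dose, duration | Partly; no event description, seriousness or causality |
| 3.5, Table 1, concomitant row | Medication, therapies and procedures, Visits 0 to 6 | Partly; same limits, and nothing if no treatment was given |
| 3.5, Table 1, healing check | Blister sites, Visits 4 and 6 | Only for what is noted at those sites |
| 3.6 | Withdrawn subjects are replaced whatever the reason | No; it does not require the reason to be recorded |
| 5.3 | Description of baseline and skin data | No; no AE or SAE summary is mentioned |

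No section requires all events or all deaths to be recorded, or sets out a causality assessment.

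**Step 3: what remains uncaptured.** In the visible text, an event judged unrelated that needs no drug, therapy or procedure leaves no required entry, apart from anything noted at a healing check. If an allowed drug was given, the four items in 3.3.1 are required, but nothing identifies an event as an AE or SAE.

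**Step 4: extent.** The filter covers 6 AE-recording visits (Visits 1 to 6) and 12 planned subjects (section 3.6). No event rate is given and none is assumed.

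**Step 5: would a wider definition swamp the record?** Section 5.1 gives 8 suction blisters per subject, so 8 × 12 = 96 intended blisters. Section 3.4 treats each as a planned wound: "the blister fluid will be punctured and a dressing applied to allow the wound to heal". This count does not measure the defect. It shows why the revised text should state that the intended wound is not itself an AE; only complications beyond it would then be added.

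**The case against.** The strongest reply is that this is a deliberate and proportionate choice. The definition is announced as the study's own and the key word is underlined. The product is petrolatum on one forearm, there are 12 subjects, and no statistical tests are planned. In a split-body design each subject is both treated and control, so systemic events cannot be compared between arms however they are recorded. Small numbers also limit what complete recording can show: with no events in 12 subjects, the one-sided 95% upper bound on the event probability is still 1 − 0.05^(1/12) = 0.22. Events correctly judged unrelated are not harms of the intervention, so the real loss is confined to misjudged events. A death would end participation and lead to replacement, so it would hardly go unnoticed. Finally, recording goes to a form in Appendix 3 that is listed by title only and may hold causality or other-event fields.

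Much of this stands as a limit on size. The impact is small, no efficacy description changes, and what the forms capture is unknown. Section 6.2 does not forbid recording unrelated events; it only does not require it. That causality is judged before recording is an inference from the definition. The note in 6.2 excluding planned hospitalization for a pre-existing condition would be largely redundant under a related-only rule, which suggests that the text was not written with one consistent rule in mind.

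None of it removes the point. Without a between-arm comparison for systemic events, causality rests on individual judgement, which can be reviewed only if the event was recorded. That a death would be noticed does not mean that it must be recorded as an SAE. If the form is broader than 6.2, form and definition disagree and need reconciling. The protocol gives no reason for the restriction.

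**Conclusion.** The concern holds as a reading of section 6.2: events judged unrelated, including serious and fatal ones, need not be recorded as AEs or SAEs, and no other visible section changes that. It should be corrected, since the correction is cheap and makes causality judgements open to review.

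The effect is confined to the harms record of a small descriptive study, and the number of events affected cannot be estimated. Confidence is high about the wording. It is lower about what the study will in practice capture, because the content of Appendices 3 and 4 is not available. The conclusion assumes that staff follow section 6.2 as written.

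**What to change.** **In section 6.2**

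- Remove the relatedness condition. Keep the existing types of event, counted from Visit 1 to the last visit regardless of cause.
- Base the SAE definition on this revised AE definition.
- Record relatedness as two separate items, one for the product and one for the suction-blister procedure, with arm and area for local events.
- As a clarification only, state that the intended blister wound is not itself an AE, and that untoward blister-site events beyond it are, including those found at the Visit 4 and Visit 6 healing checks. Keep this consistent with Appendices 3 and 4, which may already settle it.

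**In section 5.3**

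- Add a descriptive listing of AEs and SAEs with these items.

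The cost is a few sentences in 6.2 and one in 5.3. The AE page needs new items only if the form in Appendix 3 lacks them. The downside is a few more AE entries in 12 subjects; the clarification keeps the 96 intended wounds out. The outcome measurements and their descriptive analysis do not change.
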